3 OUTCOMES AND ENDPOINTS

OUTCOMES	ENDPOINTS
Primary	
1.1 Change in amount of moderate to vigorous physical activity from baseline to 48 weeks after first group session	The participant's moderate to vigorous physical activity will be measured by triaxial accelerometry. Results will be reported in minutes, with higher numbers indicating a higher amount of moderate to vigorous physical activity.
1.2 Change in the dietary risk assessment score from baseline to 48 weeks after first group session	The participant's dietary intake will be assessed using the dietary risk assessment, which includes 54 items. The dietary risk assessment measures the healthiness of a participant's eating habits. Score ranges from 0 to 108, with higher scores associated with less healthy dietary intake.
1.3 Change in veggie meter score from baseline to 48 weeks after first group session	The participant's nutrition will be assessed using the veggie meter, which uses light reflectance spectroscopy to provide an estimate skin carotenoid composite score. Score ranges from 0 to 800, with higher scores associated with greater fruit and vegetable intake.
Secondary	
2.1 Change in BMI from baseline to 48 weeks after first group session	The participant's BMI is calculated as weight (kg) divided by height (cm).
2.2 Change in weight from baseline to 48 weeks after first group session	The participant's weight will be measured using a digital scale.
2.3 Change in waist-to-hip ratio from baseline to 48 weeks after first group session	The participant's waist to hip ratio is calculated by using the mean of two waist circumference measurements divided by mean of two hip circumference measurements. Waist circumference will be measured at the midpoint between the upper iliac crest and lower costal margin in the midaxillary line. Hip circumference will be measured at the maximum width of the buttocks or gluteo-femoral fold.
2.4 Change in percent body fat from baseline to 48 weeks after first group session	The participant's percent body fat is measured using lange skinfold calipers. The final measurement will be the mean of three measurements on the right side of the body.
2.5 Change in in blood pressure (systolic blood pressure/diastolic blood pressure) from baseline to 48 weeks after first group session	The participant's blood pressure is measured using an electronic sphygmomanometer. The final measurement will be the mean of three measurements.

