3.39 Change in the Self Efficacy for Exercise Scale from baseline to 48 weeks after first group session	The participant's perceived self-efficacy for healthy exercise will be measured using the Self-Efficacy for Exercise Scale, which includes 9 items on a 11-point scale. Scores range from 0 to 90, with higher scores associated with higher self-efficacy for exercise.
3.40 Change in amount of moderate to vigorous physical activity from baseline to 16 weeks after first group session	The participant's moderate to vigorous physical activity will be measured by triaxial accelerometry. Results will be reported in minutes, with higher numbers indicating a higher amount of moderate to vigorous physical activity.
3.41 Change in amount of moderate to vigorous physical activity from baseline to 32 weeks after first group session	The participant's moderate to vigorous physical activity will be measured by triaxial accelerometry. Results will be reported in minutes, with higher numbers indicating a higher amount of moderate to vigorous physical activity.
3.42 Change in the dietary risk assessment score from baseline to 16 weeks after first group session	The participant's dietary intake will be assessed using the dietary risk assessment, which includes 54 items. The dietary risk assessment measures the healthiness of a participant's eating habits. Score ranges from 0 to 108, with higher scores associated with less healthy dietary intake.

OUTCOMES	ENDPOINTS
3.43 Change in the dietary risk assessment score from baseline to 32 weeks after first group session	The participant's dietary intake will be assessed using the dietary risk assessment, which includes 54 items. The dietary risk assessment measures the healthiness of a participant's eating habits. Score ranges from 0 to 108, with higher scores associated with less healthy dietary intake.
3.44 Change in veggie meter score from baseline to 16 weeks after first group session	The participant's nutrition will be assessed using the veggie meter, which uses light reflectance spectroscopy to provide an estimate skin carotenoid composite score. Score ranges from 0 to 800, with higher scores associated with greater fruit and vegetable intake.

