8 STUDY ASSESSMENTS AND PROCEDURES

8.1 ENDPOINT AND OTHER ASSESSMENTS

The procedures and assessments described in this section will be performed at the time points described in the schedule of activities in section 1.3.

Endpoint Assessments

Superwoman Schema Questionnaire

The participant's endorsement of Superwoman Schema will be measured using the [name] Superwoman Schema Questionnaire, which includes 35 items, divided in 5 subscales, on a 4-point scale, ranging from 0 to 3. The [name] Superwoman Schema Questionnaire measures obligation to present an image of strength, obligation to suppress emotions, resistance to vulnerability, intense motivation to succeed, obligation to help others. There are 5 different subscales for the superwoman schema, so participants will report 5 different scores. Score ranges for each subscale are 0-18 (strength), 0-21 (suppress emotions), 0-21 (resistance to vulnerability), 0-18 (motivation to succeed), 0-27 (obligation to help others), with higher scores associated with a greater endorsement of the selected superwoman schema scale characteristic.

This questionnaire will be performed at telephone screening and 16, 32, and 48 weeks post first group session. The data will be entered electronically by the patient through REDCap survey; however, paper copies of the questionnaire may be used if necessary.

Perceived Stress Scale

The participant's general stress will be measured using the PSS-14, which includes 14 items on a 5-point scale. Scores range 0-56, with higher scores indicating greater perceived stress.

This questionnaire will be performed at telephone screening and 16, 32, and 48 weeks post first group session. The data will be entered electronically by the patient through REDCap survey; however, paper copies of the questionnaire may be used if necessary.

Actigraphy

Participants will be given a triaxial ActiGraph Activity Monitor at baseline and 16, 32, and 48 weeks post first group session. Participants will be instructed to wear the ActiGraph Activity Monitor for 7 consecutive days. Participants will be instructed how to wear the ActiGraph Activity Monitor and special instructions for care by study personnel.

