For the purposes of this study, the participant's moderate to vigorous physical activity will be measured. Moderate to vigorous physical activity is defined as activities that are strenuous enough to burn off three to six times as much energy per minutes as one does when sitting quietly, or exercises that clock in at 3 to 6 METs.

Dietary Risk Assessment

The participant's dietary intake will be assessed using the dietary risk assessment, which includes 54 items. The dietary risk assessment measures the healthiness of a participant's eating habits. Score ranges from 0 to 108, with higher scores associated with less healthy dietary intake.

This questionnaire will be performed at baseline and 16, 32, and 48 weeks post first group session. The data will be entered electronically by the patient through REDCap survey; however, paper copies of the questionnaire may be used if necessary.

Veggie Meter

The participant's fruit and vegetable intake will be measured by the participant's skin carotenoids. The Veggie Meter uses a pressure-mediated reflection spectroscopy device to measure these carotenoids. Study personnel will calibrate the Veggie Meter as needed, and then ask the participant to wash their hands with soap and water. The participant will then place their finger in the cradle of the meter, and will hold it there until the scan is complete.

The Veggie Meter procedure will be performed at baseline and 16, 32, and 48 weeks post first group session.

Weight and Height

The participant's weight will be measured using an electronic scale. Weight will be converted to kilograms to calculate participant BMI. The participant's height will be measured to the nearest centimeter to calculate participant BMI.

Weight will be performed at baseline and 16, 32, and 48 weeks post first group session. Height will be performed at baseline, and is optional to perform at 16, 32, and 48 weeks post first group session.

Hip Circumference

Hip circumference will be measured at the maximum width of the buttocks or gluteo-femoral fold. Two measurements will be recorded by study personnel. The mean of these measurements will be used for the waist-to-hip ratio.

Hip circumference will be measured at baseline and 16, 32, and 48 weeks post first group session.

Waist Circumference

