9 STATISTICAL CONSIDERATIONS

9.1 STATISTICAL HYPOTHESES

Primary Endpoints:

For each primary outcome (MVPA, dietary risk, and veggie meter), at each of 16, 32, and 48 weeks, the statistical hypotheses are:

H0: The change in the outcome does not differ between intervention and control groups.

HA: The change in the outcome does differ between intervention and control groups.

Specifically, it is expected that AAW participating in an 8-session culturally relevant mindfulness intervention plus an exercise and nutrition education CM risk-reduction intervention will have greater sustained improvement in exercise and healthy eating behaviors at 16, 32, and 48 weeks post first intervention session, compared to AAW in an attention-control exercise and nutrition education CM risk-reduction intervention without mindfulness.

Secondary Endpoints:

For each secondary outcome (CM risk biomarker), at each of 16, 32, and 48 weeks, the statistical hypotheses are:

H0: The change in the outcome does not differ between intervention and control groups.

HA: The change in the outcome does differ between intervention and control groups.

It is hypothesized that AAW participating in an 8-session culturally relevant mindfulness intervention plus an exercise and nutrition education CM risk-reduction intervention will have greater reduction in CM risk biomarkers at 16, 32, and 48 weeks post first intervention session, compared to AAW in an attention-control exercise and nutrition education CM risk-reduction intervention without mindfulness.

Tertiary Endpoints:

Tertiary outcomes are self-reported mindfulness, stress management, positive reappraisal, self-regulation, and self-efficacy mediate effects of the intervention on exercise and nutrition.

For each tertiary outcome, at each of 16, 32, and 48 weeks, the statistical hypotheses are:

H0: The change in the outcome does not differ between intervention and control groups.

HA: The change in the outcome does differ between intervention and control groups.

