The primary endpoint at 48 weeks post first group session is tested at a significance level of 0.05; the other two timepoints will be tested using a Bonferroni correction of a two-sided 0.025 ($=0.05/2$) significance level. A compound symmetry correlation structure is assumed across all timepoints in our calculations. Based on pilot data, correlation parameters are 0.35 for BMI, 0.11 for WHR and -0.45 for A1C. With 80 participants per group (total of 160), statistical power is 85% to detect an effect size of 0.56 for BMI and exceeds 95% to detect an effect size of 0.45 for A1C and 0.59 for waist-hip ratio at each post-baseline time point.^{76,94} In tertiary endpoints, it is hypothesized that mediation of the intervention effect on the primary outcomes (exercise and healthy eating) by the tertiary outcomes (improvements in self-reported mindfulness, stress management, positive reappraisal, self-regulation, and self-efficacy). [In simulations of power for mediation tests, Fritz and Mackinnon⁹⁵ found that when effect sizes (standardized regression coefficients) relating the intervention to the mediator and the mediator to the outcome are all ≥ 0.26 (small- medium, according to Cohen's [1988] definition)⁹⁶, the sample size ($n=160$)

is adequate for at least 80% power. If either effect size is much smaller (simulations used 0.14), the study will be underpowered.

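### The only definition of the primary activity endpoint stops at 6 METs, so as written the most strenuous minutes add nothing to a measure named moderate to vigorous

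*Combined protocol and SAP*

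**What the plan says.** Section 3 lists primary outcome 1.1 as "Change in amount of moderate to vigorous physical activity from baseline to 48 weeks after first group session". The endpoint column names triaxial accelerometry and adds: "Results will be reported in minutes, with higher numbers indicating a higher amount of moderate to vigorous physical activity". The 16- and 32-week changes are tertiary outcomes 3.40 and 3.41.

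Section 8.1, Actigraphy, gives the device and schedule ("Participants will be given a triaxial ActiGraph Activity Monitor at baseline and 16, 32, and 48 weeks post first group session") and asks for seven consecutive days of wear. It then defines MVPA for this study in two forms. The first is in terms of energy: "activities that are strenuous enough to burn off three to six times as much energy per minutes as one does when sitting quietly". The second, offered as an alternative in MET units, reads "or exercises that clock in at 3 to 6 METs". Both forms have a lower limit of 3 and an upper limit of 6.

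Section 9.4.2 tests MVPA at the 0.05 level with the linear mixed model of section 9.4.1. Section 9.1 states the expected result as "greater sustained improvement in exercise and healthy eating behaviors" in the HARMONY arm.

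**The concern.** A measure called moderate to vigorous should include the most vigorous activity. This definition leaves it out. The documents do not say at what intensity vigorous activity begins, but the conflict does not depend on that. Wherever it begins, activity above 6 METs is more strenuous than everything inside the 3 to 6 band.

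The measure is a primary outcome. It also supplies the 16- and 32-week activity outcomes and is one of the outcomes in the mediation analyses of section 9.4.8. An analyst who follows the name and one who follows the definition would count different minutes for any participant with time above 6 METs. That choice should not be open once the data are in hand.

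**Working it through.** **Step 1: is the limit lifted anywhere?** The places that mention MVPA or vigorous exercise, side by side:

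| Place | What it gives | Intensity limits |
|---|---|---|
| Section 3, outcomes 1.1, 3.40, 3.41 | device, minutes, direction of score | none |
| Section 5.1, inclusion criterion 3a | self-reported weekly exercise minutes | none |
| Section 5.1, inclusion criterion 7 | able and willing to do such exercise | none |
| Section 8.1, Actigraphy | definition for this study | 3 to 6, stated twice |
| Sections 9.1, 9.4.1, 9.4.2 | hypothesis, model, test | none |

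Section 8.1 is the only definition. No section gives an accelerometer cut-point or a scoring algorithm that would override it.

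**Step 2: what the rule does to one participant.** Let M be minutes at 3 to 6 METs and V be minutes above 6 METs, with dM and dV their changes from baseline.

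- Capped change (section 8.1 as written) = dM.
- Uncapped change (all time at or above 3 METs) = dM + dV.
- The capped score falls while the uncapped score rises exactly when dM < 0 and dV > -dM.

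The documents give no distribution of MVPA, so every value below is assumed, for illustration only.

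| (M, V) at baseline | (M, V) at follow-up | dM | dV | Capped | Uncapped |
|---|---|---|---|---|---|
| (20, 0) min/day | (15, 10) | -5 | +10 | -5 | -5 + 10 = +5 |
| (20, 10) min/day | (25, 0) | +5 | -10 | +5 | 5 - 10 = -5 |
| (100, 0) min/week | (100, 40) | 0 | +40 | 0 | 0 + 40 = +40 |
| (60, 0) min/week | (40, 60) | -20 | +60 | -20 | -20 + 60 = +40 |

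The third row is the simplest case: exercise added only above 6 METs leaves the capped score unchanged. Reversal of sign needs both conditions, as in rows 1 and 4. Row 2 shows that it can run the other way.

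**Step 3: what can be said about the arms?** No size or direction follows. The documents give no MVPA mean, standard deviation or effect size, and no exercise intensities. Sections 6.1.1 and 6.1.2 give both arms the same type of exercise session under the same personal trainer. That does not prove equal change above 6 METs, but neither does anything point to a difference. The planned estimate is also not a difference in raw mean changes: section 9.4.1 adjusts for the baseline value, which the cap alters too.

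**Step 4: stated power.** Section 9.2 reports "statistical power is 85% to detect an effect size of 0.56 for BMI" and more than 95% for A1C and waist-hip ratio. None of these figures concerns MVPA, so there is no stated figure to reproduce or correct here.

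**The case against.** The strongest defence is that the sentence in section 8.1 is a lay description, not a scoring rule. Its style is informal, there is no cut-point, and section 3 does not say whether minutes are per day or per week. Nobody could score an ActiGraph file from this text alone, and the scoring actually used may have no ceiling. This stands as a limit on what can be claimed about the results. It does not rescue the text: the upper limit appears in both forms of the definition, and a reader has nothing else to go by.

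Four stronger readings are tempting, and the documents do not support them.

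- A reader might infer that section 8.1 contradicts the statement in section 3 that higher numbers mean more MVPA. Formally it does not. With the capped definition inserted, more minutes at 3 to 6 METs is more MVPA as defined. The conflict is between name and definition.
- A reader might infer that any increase in intense exercise is scored as a fall. It is so scored only if minutes at 3 to 6 METs drop while minutes above 6 METs rise by more.
- A reader might infer that the comparison is biased for or against HARMONY. Step 3 shows why no direction can be given.
- A reader might infer a loss of stated power. No power is stated for MVPA.

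**Conclusion.** The definition is wrong as written. It limits a primary endpoint named moderate to vigorous to 3 to 6 METs and gives zero credit to anything more strenuous. Confidence is high as to the wording. The consequence for individual scores is exact arithmetic but conditional on the rule being applied as written and on participants having time above 6 METs.

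That such time belongs in the total rests on the ordinary meaning of the endpoint's name, since no section sets a threshold for vigorous activity. The effect on the between-arm result is undetermined in size and direction and may be zero. The point should be corrected because a primary endpoint's definition conflicts with its name, not because a bias has been shown.

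**What to change.** In section 8.1, define MVPA as all minutes at or above the protocol's own lower bound of 3 METs, with no upper limit, and name the matching accelerometer cut-point. If a ceiling is really intended, say so and rename the endpoint to match. Score all baseline, 16-, 32- and 48-week ActiGraph files by that one rule before unblinding.

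The cost is a change of wording and the scoring, or re-scoring, of files that the trial collects anyway. No new data, visits or participants are needed.

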Waist circumference will be measured at the midpoint between the upper iliac crest and lower costal margin in the midaxillary line. Study personnel will record two waist circumference measurements. The mean of these measurements will be used for the waist-to-hip ratio.

Waist circumference will be measured at baseline and 16, 32, and 48 weeks post first group session.

IL-6 and CRP

Specimens for the measurement of IL-6 and CRP will be collected using standard venipuncture.

The phlebotomy procedure to obtain the IL-6 and CRP measurements will be completed at baseline and 16, 32, and 48 weeks post first group session.

HgbA1C

HgbA1C will be assessed using a fingerstick procedure at baseline and 16, 32, and 48 weeks post first group session.

Blood Pressure

Blood pressure will be collected by an electronic sphygmomanometer after a five-minute rest in the sitting position. Study personnel will record three blood pressure measurements, and the average value will be used for analysis.

Blood pressure will be measured at baseline and 16, 32, and 48 weeks post first group session.

Contextualized Stress Scale

The participant's racial and gendered stress exposure will be measured using the Contextualized Stress Measure, which includes 69 items on a 5-point scale. The Contextualized Stress Measure is divided into six subscales, including race/racism, burden, personal history, workplace, coping and support, and stress states. Score ranges from 0 to 345, with higher scores associated with increased stress exposure.

This questionnaire will be performed at baseline and 16, 32, and 48 weeks post first group session. The data will be entered electronically by the patient through REDCap survey; however, paper copies of the questionnaire may be used if necessary.

Network Stress Scale

The participant's indirect and self-stress will be measured using the Network Stress Scale, which includes 10 items on a 4-point scale. The Network Stress scale assesses both exposure and appraisal of events that happened to both self and close family members and friends. Higher scores represent higher exposure and appraisal. Score ranges from 0, with 10 scores associated with a higher amount of indirect and self-stress.

This questionnaire will be performed during the pre-baseline period and 16, 32, and 48 weeks post first group session. The data will be entered electronically by the patient through REDCap survey; however, paper copies of the questionnaire may be used if necessary.

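### The Veggie Meter procedure for primary endpoint 1.3, followed as written, is one scan on an unnamed finger with no averaging rule and no calibration schedule, which may leave avoidable random error in a primary outcome

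*Combined protocol and SAP*

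**What the plan says.** Section 3 lists "1.3 Change in veggie meter score from baseline to 48 weeks after first group session" among the primary outcomes. It says that the device "uses light reflectance spectroscopy to provide an estimate skin carotenoid composite score" on a scale of 0 to 800, and does not say what is combined into the composite.

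The measurement procedure is in section 8.1 under Veggie Meter. "Study personnel will calibrate the Veggie Meter as needed", the participant washes her hands, and then: "The participant will then place their finger in the cradle of the meter, and will hold it there until the scan is complete". The section gives no number of scans, no rule for combining them, no finger or hand, and no calibration schedule.

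Several secondary measures are specified more closely:

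- Hip circumference (8.1): "Two measurements will be recorded by study personnel. The mean of these measurements will be used for the waist-to-hip ratio".
- Waist circumference (8.1): "Study personnel will record two waist circumference measurements", and the mean is used.
- Blood pressure (8.1): "Study personnel will record three blood pressure measurements, and the average value will be used for analysis".
- Percent body fat (section 3, outcome 2.4): "The final measurement will be the mean of three measurements on the right side of the body".

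No replicates are stated for weight, BMI, hs-CRP, IL-6 or HbA1c.

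**The concern.** A reading that depends on how a finger sits in a cradle can be expected to vary somewhat between placements, though the documents do not say by how much. The protocol handles comparable technique-dependent readings (tape, cuff, calipers) by repeating and averaging them, and for skinfolds it fixes the side of the body. The Veggie Meter is primary and has none of these controls in the text.

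The model in section 9.4.1 adjusts for the baseline value of the endpoint. Random scan error therefore acts twice. It adds noise to the week-48 score, and it weakens the baseline score as a predictor, so that adjustment removes less variance. Section 9.2 reports power for BMI, A1C and waist-hip ratio only, so there is no documented power margin for this endpoint to absorb the loss.

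**Working it through.** **Plan's own figure.** There is none to reproduce. The documents state no standard deviation, effect size, power, correlation or repeatability for the Veggie Meter.

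**Inputs.**

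- Section 9.2: 80 completers per arm (200 enrolled, 20% attrition: 200 × 0.80 = 160) and alpha 0.05 at 48 weeks.
- Section 9.4.1: the baseline value is a covariate.
- Assumed: single-scan reliability R of 0.85 to 0.95, and true baseline-to-week-48 correlation c of 0.35 to 0.8. The lower end, 0.35, is borrowed as a sensitivity value. It is the largest positive correlation that section 9.2 gives for any outcome (BMI).

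**Formulas.** Set the variance of a single scan to 1. A share R is true between-person variance, and 1 − R is random error that is independent between scans. The covariance of baseline and week 48 is cR however many scans are averaged.

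- One scan: residual variance = 1 − (cR)².
- Mean of three: total variance T = R + (1 − R)/3, and residual variance = T − (cR)²/T.

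**Middle values, R = 0.90 and c = 0.7.** Here cR = 0.63 and (cR)² = 0.3969.

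- One scan: 1 − 0.3969 = 0.603.
- Three scans: T = 0.90 + 0.10/3 = 0.9333, and 0.9333 − 0.3969/0.9333 = 0.508.
- Reduction: 1 − 0.508/0.603 = 15.8%. In sample-size terms, 0.6031/0.5081 = 1.187, or 18.7% more participants.

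**Range.**

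| R | c | One scan | Mean of three | Reduction | Equivalent extra participants |
|---|---|---|---|---|---|
| 0.95 | 0.35 | 0.889 | 0.852 | 4.2% | 4.4% |
| 0.85 | 0.35 | 0.912 | 0.802 | 12.0% | 13.7% |
| 0.95 | 0.6 | 0.675 | 0.631 | 6.6% | 7.1% |
| 0.90 | 0.7 | 0.603 | 0.508 | 15.8% | 18.7% |
| 0.85 | 0.8 | 0.538 | 0.386 | 28.2% | 39.2% |

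**In terms of power.** Let δ be an assumed effect in units of the true (error-free) standard deviation. The standardised effect after adjustment is δ√R divided by the square root of the residual variance. With 80 per arm, two-sided alpha 0.05 and the noncentral t distribution, at R = 0.90 and c = 0.7:

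- δ = 0.30: 63% with one scan, 71% with three.
- δ = 0.35: 77% and 83%.
- δ = 0.45: 93% and 96%.

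At the favourable corner (R = 0.95, c = 0.35) with δ = 0.30, power goes from 49.6% to 51.2%, a gain of under 2 points. A comparison without baseline adjustment, which is not the planned model, gives 77.0% and 79.8% at R = 0.90 and δ = 0.45.

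**The case against.** The strongest reply is that the protocol nowhere says that only one scan is taken. The sentence in 8.1 describes how a scan is done. The composite score in section 3 is unexplained and could already be a combination of readings. Section 8.1 is also not a complete manual: the three-reading rule for body fat stands in section 3 and has no counterpart in 8.1. This stands. The text supports a single scan only as its literal reading, so the conclusion has to be conditional.

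The contrast with the secondary measures is also partial. Averaging is stated for three of the eight secondary endpoints (2.3, 2.4 and 2.5) and not for the other five (2.1, 2.2, 2.6, 2.7 and 2.8). It would be wrong to say that secondary measures in general are averaged.

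A reader might infer that a change of finger or of calibration state between baseline and week 48 could produce a false treatment effect. The documents do not support that. The test compares arms, baseline precedes randomization, and both arms are randomized within each cohort (section 4.1). Variation of this kind that is unrelated to arm adds noise and no bias.

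Finally, the size rests on assumptions. The documents give neither reliability nor correlation, and naming the technology as pressure-mediated does not quantify placement error. The calculation also treats all error as independent between scans. Error common to a visit, including calibration state, survives averaging, so each tabulated gain is the most that could be had at those values.

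**Conclusion.** For a primary endpoint, the written procedure has no repeat, no averaging rule, no fixed finger and no calibration timing. If one scan is what is done, the mean of three would reduce the baseline-adjusted residual variance by about 4% to 28%. This assumes single-scan reliability of 0.85 to 0.95, true correlation of 0.35 to 0.8, and error independent between scans; the range is an upper value for the reason given above. The 39% sample-size equivalent belongs to one corner of the range and should not be quoted as the expected loss.

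This is an inexpensive gain in precision on one of three primary outcomes. It is not evidence that the endpoint is invalid or the arm comparison biased.

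**What to change.** In section 8.1 (Veggie Meter) and in the definition of endpoint 1.3, state that at every visit three scans are taken with the finger repositioned each time, that the same finger of the same hand is used at all visits, and that the mean is analysed. Replace discretionary calibration with calibration at the start of each visit day. Averaging deals with placement error; the calibration rule is needed for the part that all scans on a day share.

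The cost is wording, two more data fields and about a minute per visit, on the same device with the same staff. The minute is an estimate, since the documents give no scan time.

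If the change is made after enrolment has begun, record the number of scans at each visit, introduce it by whole cohort so that both arms are affected equally, and leave earlier single-scan visits as they are. If the device or a manual already combines repeated scans, state that in the protocol instead, together with the finger and the calibration timing.
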